2.3.2 KNOWN POTENTIAL BENEFITS

The primary potential benefit for research subjects in this study is the benefit of adding to medical knowledge. There is a potential benefit for symptoms of depression as well.

3 OBJECTIVES AND OUTCOME MEASURES

OBJECTIVES	Outcome Measures

Primary
 
Aim 1: To determine whether iTBS to the medial prefrontal cortex (mPFC) produces more robust changes in frontal midline theta (FMT) EEG power in people with Parkinson's disease compared with stimulation at the dorsolateral prefrontal cortex (DLPFC) or the primary sensory cortex (S1). Aim 2: A. To evaluate FMT power correlations with burden of autonomic symptoms at baseline before stimulation in Parkinson's disease. B. To evaluate FMT power correlations with burden of depression symptoms at baseline before stimulation in Parkinson's disease
	
Aim 1: Degree of change of frontal midline theta power on EEG after brain stimulation. Aim 2: Degree of association between autonomic symptoms and frontal midline theta EEG power; Degree of association between depression symptoms and frontal midline theta EEG power.

Exploratory
 
Aim 3: To evaluate the effect of iTBS on autonomic symptoms one day after, and 4 days after stimulation. Aim 4: To evaluate the effect of iTBS on depression symptoms one day after, and 4 days after stimulation.
 
Aim 5: To create a database of EEG and TMS data in people with PD for
	
1. Change in SCOPA-AUT and OHQ from before to after iTBS; 2. Change in BDI-II from before to after iTBS

OBJECTIVES	Outcome Measures
the purpose of future research into novel neurostimulation therapies for PD NMS	

4 STUDY DESIGN

4.1 OVERALL DESIGN

This is a prospective, triple crossover (three stimulation sites which will be done at separate study visits), single-blinded study design. The difference in stimulation site precludes double-blinding as the study personnel will be aware of the difference in location while running the experiment.

Aim 1: To determine whether iTBS to the medial prefrontal cortex (mPFC) produces more robust changes in frontal midline theta (FMT) EEG power in people with Parkinson's disease compared with stimulation at the dorsolateral prefrontal cortex (DLPFC) or the primary sensory cortex (S1).

Hypothesis:

H_0 : Mean change in Frontal midline theta power on electroencephalogram after iTBS to the medial prefrontal cortex will be equal to FMT changes after dorsolateral prefrontal cortex stimulation and stimulation of S1.

H_1 : Mean change in Frontal midline theta power on electroencephalogram after iTBS to the medial prefrontal cortex will be greater than FMT changes after dorsolateral prefrontal cortex stimulation and stimulation of S1.

Aim 2A: To identify associations between symptoms of autonomic dysfunction at baseline before stimulation and frontal midline theta band frequency on electroencephalogram.

H_0 : There is zero correlation between severity of autonomic dysfunction symptoms at baseline before stimulation with frontal midline theta power at baseline on electroencephalogram.

H_1 : There is a negative correlation between severity of autonomic dysfunction symptoms at baseline before stimulation with frontal midline theta power at baseline on electroencephalogram.

Aim 2B: To identify associations between symptoms of depression at baseline before stimulation and frontal midline theta band frequency on electroencephalogram.

Hypothesis:

H_0 : There is no correlation between severity of depression symptoms at baseline before stimulation with frontal midline theta power on electroencephalogram at baseline.

H_1 : There is negative correlation between depression symptoms at baseline before stimulation with frontal midline theta power on electroencephalogram at baseline.

Exploratory objectives

Aim 3: To evaluate the effect of iTBS on autonomic symptoms one day after, and 4 days after stimulation.

Hypothesis:

H_0 : Change in SCOPA-AUT and OHQ will be zero one day after stimulation and 4 days after stimulation compared to pre-stimulation.

H_1 : Change in SCOPA-AUT and OHQ will be less than zero one day after stimulation and 4 days after stimulation.

Aim 4: To evaluate the effect of iTBS on depression symptoms one day after, and 4 days after stimulation.

Hypothesis:

H_0 : Change in BDI-II will be zero one day after stimulation and 4 days after stimulation compared to pre-stimulation.

H_1 : Change in BDI-II will be less than zero one day after stimulation and 4 days after stimulation.

Aim 5: To create a database of EEG and TMS data in people with PD for the purpose of future research into novel neurostimulation therapies for PD NMS.

Hypothesis: We will maintain a de-identified database of EEG, clinical, and demographic data from people with PD undergoing iTBS.

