2.3 RISK/BENEFIT ASSESSMENT

2.3.1 KNOWN POTENTIAL RISKS

Psychological risk

Breach of confidentiality: While there is the potential for breach of confidentiality, all study personnel will minimize this risk to study subjects. All data will be de-identified before analysis, and any treatment outcome data will be treated with strict confidentiality. Electronic data will be stored on password-protected servers within the UNC School of Medicine and any hard-copy data will be stored in locked cabinets in locked offices in the UNC Department of Neurology.

Risk of embarrassment: There is a risk of distress or embarrassment for the participant if they have difficulty performing well on cognitive and physical tests. The research team will take extra care to perform these evaluations in a judgement-free manner, and provide appropriate encouragement to the participant, as is routinely done in a clinical setting. Additionally, we will request that the participant be alone in the examining room with the examiner, without care partner or other persons in the room, while performing these examinations, unless otherwise preferred by the participant, to help minimize this risk.

Physical risk:

Risk of injury and discomfort: Transcranial magnetic stimulation (TMS) is FDA approved for treatment of many neuropsychiatric symptoms in the USA. TMS is not related to electroconvulsive therapy, which applies many orders of magnitude higher stimulation electrical current. The level of electrical stimulation produced by TMS is within the range of activity that is endogenous to the brain. Furthermore, the intensity of stimulation is calibrated to the sensitivity of the individual participant such that the level of stimulation is matched to the naturally occurring brain activity in that individual. In order to monitor side effects, participants will be asked to complete an adverse effects from stimulation questionnaire after each stimulation session. Research personnel supervising the stimulation sessions will also check with the participant periodically during the stimulation session to ensure the participant is comfortable. If any side effects occur that are rated by the participant as stronger than "moderate", or the participant reports severe discomfort during stimulation, the stimulation session will be terminated immediately.

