4.3 JUSTIFICATION FOR DOSE

Transcranial magnetic stimulation (TMS) is a safe, non-invasive tool routinely used in clinical care which applies magnetic fields to the brain using coils placed on the scalp. During the first stimulation session in the study, participants will receive a motor thresholding procedure in which electrodes are attached to

the first dorsal interosseous muscle of the right hand, or another muscle on the hand or arm that is accessible to be targeted by TMS to the motor cortex. The contralateral motor cortex will be targeted by single pulses of TMS with increased stimulator output until a motor evoked potential (MEP), defined as a near-instantaneous increase in muscle activity greater than 200 microvolts, is generated. Next, the intensity of single pulse TMS will be lowered until a MEP is generated on five out of 10 pulses. This is defined as the individual's motor threshold. If MEP determination of motor threshold is not possible, the researcher will use visible twitches as a proxy for MEP. Participants will receive iTBS at 80% of their motor threshold.

Subjects will undergo iTBS to the mPFC, left DLPFC, and left primary sensory area in a triple cross-over study design. I will use a MagVenture MagPro X100 TMS device with active cooling coil. Stimulation location will be determined using established scalp coordinates for each stimulation location with the "10-20" international coordinate system ⁴²⁻⁴⁵. For the mPFC, stimulation will be done between the Fpz and Cz EEG electrode location. For left DLPFC, stimulation will be done at the F3 location using the Beam-F3 technique^{46,47}. For the primary sensory cortex, stimulation will be done 1.5cm posterior to the motor hotspot and at vertex position used for intensity calibration. Accelerated iTBS will be performed in the reclined position to reduce symptoms of orthostatic hypotension, with subjects awake and at rest. Subjects will receive bursts of 3 pulses at 50 Hz repeated at 200-msec intervals (5Hz) for two seconds^{48,49}. The two-second trains will be repeated 20 times every 10 seconds (3:30 total stimulation time), and followed by a rest period. This sequence may be repeated up to 4 times. Behavioral effects of stimulation last at least 36 hours after one stimulation session with this protocol¹.

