6.2 MEASURES TO MINIMIZE BIAS: RANDOMIZATION AND BLINDING

To control for bias, we have decided on a prospective, controlled, triple crossover (three stimulation locations at separate study visits) study design. Participants will be blinded as to stimulation location, and each participant will experience stimulation at all locations. Each participant will have all rating scales performed by the same rater. Potential confounding factors, such as age, disease duration, cognitive function, and overall disease severity will be evaluated and controlled for, as indicated, in the final statistical models.

Stimulation order will be randomized and counter-balanced. Participants are assigned a study ID number and randomized upon signing the informed consent form. Subject ID will be entered into the randomization algorithm by the research assistant. A randomization table will be generated by a computerized script that randomizes and counterbalances by ID, generating an Excel spreadsheet. We will perform complete counterbalancing, there are 6 potential sequences (mPFC-DLPFC-S1, mPFC-S1-DLPFC, DLPFC-mPFC-S1, DLPFC-S1-mPFC, S1-mPFC-DLPFC, S1-DLPFC-mPFC) and a plan for 48 participants. Every effort will be made to completely counterbalance our sample. Thus effects of stimulation order will be minimized.

Treatment Assignment Procedures: Participants will receive stimulation to the medial prefrontal cortex, the dorsolateral prefrontal cortex, and the primary sensory cortex. The order of stimulation will be randomized and counterbalanced. Randomization will be performed using a script that generates a

spreadsheet. Randomization will be done after the screening visit is completed, before initiation of stimulation sessions.

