8.3.5 ADVERSE EVENT REPORTING

All AEs will be captured and recorded at each stimulation visit in person, and one day after, and four days after each stimulation visit over telephone. The AE report form will be completed by the researcher, and will include details about the stimulation, what is known about previous reported side effects, if the AE occurred in temporal relation to the stimulation, whether the AE improves or completely resolves once stimulation is ceased, whether the AE is worsening of a baseline symptom, and whether the AE is related to concurrent medication or medical condition. This form will be presented to the PI who will review and sign the form. Completed forms will be placed in the participant's file in the study binder. AEs will also be documented in the AE log, which will also document the date, severity, relationship to treatment (as determined by the PI), actions taken, and outcome. Medical conditions and symptoms present prior to start of stimulation on the day of the visit will not be considered an AE.

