9 STATISTICAL CONSIDERATIONS

Statistical planning and analysis will be done by the PI [name] in collaboration with [name] and consultation with biostatistician [name].

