All clinical data and logs of collected data will be recorded on paper forms and then transferred to computerized data forms. Paper forms will be stored in double-locked storage. All computerized records will be password protected and HIPAA compliant. Electronic study data will be stored as Excel spreadsheets and kept on School of Medicine (SOM) IT secure network, and on a cloud-based UNC SOM approved HIPAA-compliant server. Study data may also be stored in the UNC REDCap system. This is a secure, password-protected, HIPAA compliant web application developed by the NIH that is widely used in clinical research. A data dictionary will be created by the study coordinator and the PI. Data accuracy and completion will be monitored periodically by the PI using SAS software to look for missing data points and out of range values. Confidentiality will be maintained by storing all collected study information labeled with only the anonymous study identification numbers. Electronic data will be stored using only study identification numbers in password protected databases and encrypted endpoints. The linked identified data will be stored separately from the deidentified research data on the SOM IT secure network. No individual identifying information will be included in any clinical reports or sample logs in this study.

Stored data will include all data collected during the course of the study, and data obtained from the participants' clinical chart including autonomic testing parameters, clinical scales, questionnaires, co-

morbid medical conditions, date of PD diagnosis, age, concomitant medications, prior surgeries. The PI, co-Is, and research assistant will be in charge of data management.

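### Nothing in the plan keeps offline EEG processing masked to stimulation site or pre/post status, which leaves an avoidable route for bias into the Aim 1 contrast

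*Combined protocol and SAP*

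**What the plan says.** - **Masking.** Section 6.2: "Participants will be blinded as to stimulation location". No other party is described as masked. Section 4.1 gives the reason for not double-blinding: "study personnel will be aware of the difference in location while running the experiment".
- **Analysis.** Section 9: "Statistical planning and analysis will be done by the PI", together with a collaborator and in consultation with a biostatistician. No masking is stated for any of the three.
- **The PI's contact with sessions.** Section 8.3.5 has the adverse-event form include details of the stimulation and continues: "This form will be presented to the PI who will review and sign the form". Sections 4.3 and 6.1 are written in the first person ("I will use a MagVenture MagPro X100 TMS device with active cooling coil"), which suggests, without stating it formally, that the protocol's author delivers stimulation.
- **Allocation and data handling.** Section 6.2: "Subject ID will be entered into the randomization algorithm by the research assistant". Section 10.1.10.1: "The PI, co-Is, and research assistant will be in charge of data management".
- **Coding.** Section 2.3.1: "All data will be de-identified before analysis". This appears under confidentiality and concerns participant identity.
- **Outcome.** Section 8.1.2 has EEG recorded before and immediately after stimulation, with FMT power as the primary outcome. Section 9.4.1 tests it with a mixed model containing location, time and their interaction. The EEG text covers acquisition only. It gives no artefact-rejection rule, no channel set for FMT and no preprocessing steps.

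**The concern.** Whoever positions the coil must know the site. Whoever later cleans a stored EEG file need not. The plan's stated reason for single-blinding stops at the end of the session, but the plan adds no masking after that point.

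This matters because resting EEG usually needs judgement about which segments or components to drop, and the plan itself expects artefact: eye and submental muscle channels are recorded, and section 5.2 excludes tremor or dyskinesia that the PI judges would interfere with the EEG. The Aim 1 alternative is directional in favour of mPFC, and the comparators are other stimulated sites. If processing choices differed even slightly between mPFC and the other recordings, or between pre and post recordings in a site-dependent way, the difference would pass straight into the Location-by-time contrast. Randomizing the order of sites does not remove that kind of bias.

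**Working it through.** **1. Which reason covers which step**

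| Step | Must the person know the site? | What the plan says on masking |
|---|---|---|
| Delivering stimulation | Yes | Section 4.1: personnel unmasked |
| Receiving stimulation | No | Section 6.2: participant masked |
| Processing stored EEG and extracting FMT | No | Nothing |
| Statistical analysis | No, until values are locked | Nothing; PI-led (section 9) |

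De-identification does not fill the gap. A file labelled with a study number can still show site, visit and pre/post status.

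**2. The plan's own Aim 1 figure**

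Section 9.2 gives power 0.82 with N = 45, f² = 0.15, α = 0.05 and 3 predictors. Noncentrality is 0.15 × 45 = 6.75 and residual df is 45 − 3 − 1 = 41. A one-sided t test of a single coefficient gives 0.819, so the figure reproduces. The two-sided version gives 0.718. This has no bearing on masking; it shows only that the stated power corresponds to a one-sided test.

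**3. Illustration of what a processing bias would do**

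The documents give no bias size, so the values of b below are assumptions. Let b be a shift favouring mPFC over both other sites, in SDs of the session-level pre-to-post change, with no true site effect and n = 48. Session changes within a person are taken as uncorrelated, as a participant-level random-intercept model implies, because the intercept cancels from each change.

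- Pairwise contrast: SE = √(2/48) = 0.204. One-sided error = 1 − Φ(1.645 − b/SE).
- Interaction test on 2 df: the site shifts, centred, are 2b/3, −b/3 and −b/3, with sum of squares 2b²/3. Noncentrality = 48 × 2b²/3 = 32b², compared with the 5% critical value of χ² on 2 df.

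| Assumed b | b/SE | One-sided pairwise | Two-sided pairwise | 32b² | 2-df interaction |
|---|---|---|---|---|---|
| 0.1 | 0.49 | 12% | 8% | 0.32 | 7.5% |
| 0.2 | 0.98 | 25% | 17% | 1.28 | 16% |
| 0.3 | 1.47 | 43% | 31% | 2.88 | 31% |

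The last column is closest to section 9.4.1, which plans a likelihood-ratio or Wald test in the interaction model.

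**4. Sensitivity to the unit**

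If b is instead measured in SDs of the within-person difference between two sites, a paired t test with n = 48 gives one-sided error of 16.8%, 39.0% and 65.7%, and two-sided error of 10.4%, 27.4% and 53.0%, for b = 0.1, 0.2 and 0.3. The two units coincide when session changes correlate at 0.5, since √(2 × (1 − 0.5)) = 1. Positive correlation therefore makes a given bias more damaging.

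**5. Which aims are exposed**

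Aim 1 compares pre-to-post change across sites and is exposed. Aim 2 relates symptoms to FMT before any stimulation (sections 3 and 9.1) and contains no site contrast.

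**The case against.** The strongest reply is that the documents show an omission, not an unmasked process. That stands. A reader might infer that the staff who run the sessions also process the EEG. No section says so: the sentence in section 4.1 is limited to running the experiment, and section 9 concerns statistical planning and analysis, not artefact handling. The table of contents also lists a section on key roles and governance that is absent from the text available here, and duties could be assigned in it. A reader might likewise take the PI to be the sole analyst, but section 9 names a collaborator and a consulting biostatistician too.

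A second reply is that discretionary segment rejection is assumed. If the pipeline is fully automated, most of the route closes. That is fair, and it is why masking alone is an incomplete remedy: a fixed pipeline has to be specified as well. As written, the plan specifies neither.

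A third reply is that the error rates rest on invented biases. They do, and the one-sided pairwise column looks worse than the interaction test the plan describes. They should be read only as showing the direction and rough sensitivity.

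What survives is that section 6.2, the section devoted to minimizing bias, masks participants only, and nothing elsewhere extends masking to stored EEG.

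**Conclusion.** The point holds as an avoidable gap and is best classed as a cheap improvement. The reason given for single-blinding does not reach offline processing. Nothing in the plan keeps the processor unaware of site or pre/post status, no artefact rule limits discretion, and the PI, who sees session details through the adverse-event forms, leads the analysis.

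Three stronger readings are not supported. First, that bias has occurred or will occur: the documents give no evidence on its presence or size, and the figures of 7.5% to 31% depend on assumed shifts of 0.1 to 0.3 SD, uncorrelated session changes and n = 48. Second, that every primary aim is affected: FMT is the outcome for Aims 1 and 2, but only Aim 1 has a site contrast. Third, that renaming files would prevent the problem: codes help only if recording times are removed and the key is kept from the processor, and even then they reduce the risk without eliminating it.

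**What to change.** Add to sections 6.2 and 9.4.1:

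1. State which role processes the EEG.
2. Before processing, give each EEG file a random code and strip recording times, so that site, visit and pre/post status are hidden. A computerized script already produces the allocation spreadsheet in section 6.2; a similar short script can produce the codes.
3. Carry out preprocessing and FMT extraction by one fixed, prespecified pipeline, including the artefact-rejection rule and the FMT channels.
4. Lock the FMT values under the code.
5. Have the key held by an existing team member who does not process EEG, for example the consulting biostatistician, and merge it only after the lock. The holder should be named by role, because the research assistant handles allocation and also shares data management.

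Cost: a short script, a paragraph or two of text, a small file-handling step and a key to protect. The documents give no cost figure, so calling this cheap is a judgement. The sample size of 48, α, planned power, visits and stimulation are unchanged.

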4.2 SCIENTIFIC RATIONALE FOR STUDY DESIGN

The stimulation locations in the current study design were chosen due to prior data implicating the medial prefrontal cortex and dorsolateral prefrontal cortex in both autonomic and affective disorders. Primary sensory cortex was chosen as a control site due to its limited involvement in Parkinson's disease pathology, autonomic function, and depression. We chose a control stimulation location rather than sham stimulation because participants will be able to feel the difference between real and sham stimulation in this crossover design. A triple crossover design was chosen to maximize study recruitment and minimize subject variability between stimulation arms.

4.3 JUSTIFICATION FOR DOSE

Transcranial magnetic stimulation (TMS) is a safe, non-invasive tool routinely used in clinical care which applies magnetic fields to the brain using coils placed on the scalp. During the first stimulation session in the study, participants will receive a motor thresholding procedure in which electrodes are attached to

the first dorsal interosseous muscle of the right hand, or another muscle on the hand or arm that is accessible to be targeted by TMS to the motor cortex. The contralateral motor cortex will be targeted by single pulses of TMS with increased stimulator output until a motor evoked potential (MEP), defined as a near-instantaneous increase in muscle activity greater than 200 microvolts, is generated. Next, the intensity of single pulse TMS will be lowered until a MEP is generated on five out of 10 pulses. This is defined as the individual's motor threshold. If MEP determination of motor threshold is not possible, the researcher will use visible twitches as a proxy for MEP. Participants will receive iTBS at 80% of their motor threshold.

Subjects will undergo iTBS to the mPFC, left DLPFC, and left primary sensory area in a triple cross-over study design. I will use a MagVenture MagPro X100 TMS device with active cooling coil. Stimulation location will be determined using established scalp coordinates for each stimulation location with the "10-20" international coordinate system ⁴²⁻⁴⁵. For the mPFC, stimulation will be done between the Fpz and Cz EEG electrode location. For left DLPFC, stimulation will be done at the F3 location using the Beam-F3 technique^{46,47}. For the primary sensory cortex, stimulation will be done 1.5cm posterior to the motor hotspot and at vertex position used for intensity calibration. Accelerated iTBS will be performed in the reclined position to reduce symptoms of orthostatic hypotension, with subjects awake and at rest. Subjects will receive bursts of 3 pulses at 50 Hz repeated at 200-msec intervals (5Hz) for two seconds^{48,49}. The two-second trains will be repeated 20 times every 10 seconds (3:30 total stimulation time), and followed by a rest period. This sequence may be repeated up to 4 times. Behavioral effects of stimulation last at least 36 hours after one stimulation session with this protocol¹.

A high-density EEG net (128 electrodes including electrooculography electrodes; MagStim EGI, Inc.) and two submental electromyography (EMG) electrodes will be applied. Continuous qEEG recording will be performed for 8 minutes while the participant is asked to keep their eyes open and focused on a crosshairs. Sampling rate during the continuous recording will be 1 kHz with Cz as the reference and a channel between Cz and Pz as ground, using an EGI system with SDK AmpServer Pro (Geodesic, Eugene, Oregon). Collecting EEG with TMS does not pose any additional risk over TMS on its own. EEG electrodes are placed on the scalp to record electrical brain activity. EEG does not involve brain stimulation and is used purely as a neuroimaging tool, posing minimal risk.

